NCT04359810

Protocol (Population A) V 17AUG2020

Long title: A Phase 2, Randomized Clinical Trial to Evaluate the Efficacy and Safety of Human Anti-SARS-CoV-2 Convalescent Plasma in Severely Ill Adults with COVID-19 (AAAS9924)

Short title: Population A: Convalescent Plasma in Severe COVID-19 Clinical

Phase: 2 IND Sponsor: [name]

Principal Investigator: [name], MPH

Conducted by: Columbia University

Sample Size: 220

Study Population: Subjects aged ≥ 18 years with severe COVID-19

Study Duration: Approximately 1 year.

Study Design: Randomized blinded phase 2 trial to assess the efficacy and safety of anti-SARS-CoV-2 plasma among adults with severe COVID-19. A total of 220 eligible subjects will be randomized in a 2:1 ratio, stratified by country (US, Brazil) to receive either convalescent plasma qualitatively positive for SARS-CoV-2 antibody (anti-SARS-CoV-2 plasma) or non-convalescent fresh frozen plasma (control plasma). The patient and the study clinician assessing the clinical outcome will be blinded to the treatment arm.

The following will be assessed in all subjects:

Safety and efficacy: Day 0 (baseline) to Day 28.

Study Agent:

- Anti-SARS-CoV-2 convalescent plasma (1 unit; ~200-250 mL collected by apheresis from a volunteer who recovered from COVID-19 (collection and qualification covered by IRB protocol AAAS9845 (Convalescent plasma donors)) and was found to be a qualitatively positive for SARS-CoV-2 antibody ("anti-SARS-CoV-2 plasma").
- Control plasma: 1 unit of standard plasma collected prior to December 2019 Protocol (Population A) V 17AUG2020

Primary Efficacy Objective: To evaluate the efficacy of treatment with anti-SARS-CoV-2 plasma versus control plasma with respect to Day 28 severity outcome.

Primary Endpoint: The primary endpoint is Day 28 severity outcome on a seven-category scale:

1. Not hospitalized with resumption of normal activities
2. Not hospitalized, but unable to resume normal activities
3. Hospitalized, not requiring supplemental oxygen
4. Hospitalized, requiring supplemental oxygen
5. Hospitalized, requiring high-flow oxygen therapy or noninvasive mechanical ventilation
6. Hospitalized, requiring extracorporeal membrane oxygenation (ECMO), invasive mechanical ventilation, or both
7. Death

Primary Safety Objective: To evaluate the safety and tolerability of treatment with anti- SARS-CoV-2 plasma versus control (control plasma) in adults with severe COVID-19.

Primary Safety Endpoints:

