1. To compare duration of need for supplemental oxygen and/or mechanical ventilation between recipients of the anti-SARS-CoV-2 plasma and control plasma.
2. To compare duration of hospitalization between recipients of the anti-SARS-CoV-2 plasma and control plasma.

3. To compare in-hospital and 28-day mortality between recipients of the anti-SARS-CoV-2 plasma and control plasma.

Ancillary Endpoints:

1. To compare the proportion and duration of SARS-CoV-2 PCR positivity (RT PCR) between recipients of the anti-SARS-CoV-2 plasma and control plasma at days 0, 7, and 14.
2. To compare the levels of SARS-CoV-2 RNA between recipients of the anti-SARS-CoV-2 plasma and control plasma at days 0, 7, and 14.
3. To compare genetic differences between recipients of the anti-SARS-CoV-2 plasma and control plasma to explore possible associations with poor outcome.
4. To compare transcriptomic differences between recipients of the anti-SARS-CoV-2 plasma and control plasma at Day 0, 7, and 14 to explore possible associations with poor outcome.

Definitions

Enrolled: From time consented to participate until designated as a screen failure or have either been discontinued from the study or completed it. II. Randomized: when a study arm is assigned. III. Screen Failures: signed informed consent, but then determined to be ineligible or withdraws before being randomized. IV. Discontinued: randomized, but then withdrawn by investigator or withdraws consent. V. Completed: Subjects are considered completed when they are followed through to day 28, if they die before day 28, or are discharged prior to day 14.

Study population

Inclusion Criteria for Enrollment 1. Willing and able to provide written informed consent prior to performing study procedures or having a legally authorized representative available to do so. 2. Age ≥ 18 years. 3. Evidence of SARS-CoV-2 infection by PCR test of nasopharyngeal swab or oropharyngeal swab/tracheal aspirate sample within 14 days of randomization 4. $\text{SpO}_2 \leq 94\%$ on room air or requiring supplemental oxygen, non-invasive or invasive mechanical ventilation at screening 5. Evidence of infiltrates on chest radiography 6. Females of childbearing age and males must be willing to practice an effective contraceptive method or remain abstinent during the study period.

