- Levels of SARS-CoV-2 RNA on Days 0, 7, and 14.
- Duration of need for supplemental oxygen and/or mechanical ventilation
- Duration of hospitalization
- Mortality.

Statistical Analysis

• Efficacy Objective

1. Primary Analysis, go/no-go decision, and power consideration

The primary analysis of the endpoint will be a one-sided nonparametric stratified Mann-Whitney test; stratification is done by country (US, Brazil). A “go decision” in this phase 2 trial will be a one-sided $P < .015$, suggesting evidence of promise of the treatment arm for further investigation in a phase 3 trial. Adaptive seamless phase 2/3: The results in this proof-of-concept study will be used to plan the sample size in a Phase 3 trial, which may include the data in this Phase 2 in the final analysis using adjusted P value as in a seamless phase 2/3 trial. Details of P value adjustment and sample size calculation will be decided before the final analysis of this study data.

The calculation was based on blinded pooled data of the Day 28 outcome and an odds ratio of 1.7 under a proportional odds assumption. With a 2:1 randomization ratio and a total sample size of 219 participants (146 in convalescent plasma vs. 73 control), a onesided Mann Whitney test at 15% level will have about 82% power to detect an odds ratio of 1.7. Since the difference in power between 219 and 220 is minimal, $N=219$ can be used to justify an enrollment total of 220. We note a recent study of antiviral drug yields an odds ratio of 1.15, with 95% CI: 0.67 to 1.96, which covers our assumed odds ratio.

2. Secondary and Ancillary Analyses

All secondary and ancillary efficacy analyses will also be intent-to-treat. With a sample size of 220, assuming 20% mortality up to day 28, we expect a total of 43 events. Longitudinal data collected over multiple days during the study period (e.g., PCR positivity, RNA) will be analyzed using the framework of generalized linear mixed model. Time-to-event variables (e.g., time to death) will be analyzed using Cox proportional hazards model. Continuous variables (e.g. duration of hospitalization) will be analyzed using Mann Whitney test. Treatment effects on these variables will be estimated with 95% confidence intervals.

3. Safety Analyses

Serious adverse events will be summarized by grades and types using proportions and 95% confidence intervals for the two study arms. Relative safety profile of the two arms will be compared using Fisher's exact test.

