Day 1 ± 1 1. Vital signs 2. COVID-19 symptom screen (fevers, cough, shortness of breath) 3. Assessment of clinical status (using 7-point ordinal outcome scale) 4. New medical conditions, AE evaluation 5. Physical examination (acceptable to use clinician notes from electronic medical record) 6. CBC, comprehensive metabolic panel (abstracted from routine clinical lab results in electronic medical record) 7. Stored samples for future studies (only if feasible)

Day 3 ± 2 1. Vital signs 2. COVID-19 symptom screen (fevers, cough, shortness of breath) 3. Assessment of clinical status (using 7-point ordinal outcome scale) 4. New medical conditions, AE evaluation 5. Physical examination (acceptable to use clinician notes from electronic medical record)

Day 7 ± 2 1. Vital signs 2. COVID-19 symptom screen (fevers, cough, shortness of breath) 3. Assessment of clinical status (using 7-point ordinal outcome scale) 4. New medical conditions, AE evaluation 5. Physical examination (acceptable to use clinician notes from electronic medical record) 6. SARS-CoV-2 testing (RT-PCR) from nasopharyngeal swab (only if feasible) 7. CBC, comprehensive metabolic panel (abstracted from routine clinical lab results in electronic medical record) 8. Stored samples for future studies (only if feasible)

Day 14 ± 2 1. Vital signs 2. COVID-19 symptom screen (fevers, cough, shortness of breath) 3. Assessment of clinical status (using 7-point ordinal outcome scale) 4. New medical conditions, AE evaluation 5. Physical examination (acceptable to use clinician notes from electronic medical record) 6. SARS-CoV-2 testing (RT-PCR) from nasopharyngeal swab (only if feasible) 7. CBC, comprehensive metabolic panel (abstracted from routine clinical lab results in electronic medical record) 8. Stored samples for future studies (only if feasible)

Day 28 ± 3 1. Vital signs 2. COVID-19 symptom screen (fevers, cough, shortness of breath) 3. Assessment of clinical status (using 7-point ordinal outcome scale) 4. New medical conditions, AE evaluation 5. Physical examination (acceptable to use clinician notes from electronic medical record)

EFFICACY, VIROLOGIC AND PK MEASURES

Primary Endpoint:

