Day 28 severity outcome on a seven-category ordinal scale consisting of the following categories: 1. Not hospitalized with resumption of normal activities 2. Not hospitalized, but unable to resume normal activities 3. Hospitalized, not requiring supplemental oxygen 4. Hospitalized, requiring supplemental oxygen 5. Hospitalized, requiring high-flow oxygen therapy or noninvasive mechanical ventilation 6. Hospitalized, requiring extracorporeal membrane oxygenation (ECMO), invasive mechanical ventilation, or both 7. Death

Virologic measures:

1. Rates and duration of SARS-CoV-2 PCR positivity (RT PCR) at days 0, 7 and 14.
2. Peak quantity levels of SARS-CoV-2 RNA at days 0, 7 and 14.

RISKS AND BENEFITS

Potential benefits of treatment

The potential benefits of antiviral treatment with anti-SARS CoV-2 plasma in patients with severe COVID-19 is unknown. However, based on available evidence from use of convalescent plasma in SARS-CoV-1 patients, shortened duration of illness and improved mortality are potential benefits.

Potential benefits of clinical monitoring and virologic testing

Subjects enrolled in the study will undergo close virological monitoring that may facilitate improved understanding of viral shedding that may have benefit to the individual, their family and the community at large.

Potential risks of study procedures

1. Risks of plasma: Fever, chills, rash, headache, serious allergic reactions, transmission of infectious agents
2. Transfusion related acute lung injury (TRALI) and transfusion related circulatory overload (TACO), both of which may worsen oxygen saturation and increase work-of-breathing
3. Risks of phlebotomy: local discomfort, bruising, hematoma, bleeding, fainting
4. Total blood draws will not exceed 500 mL
5. Risks of nasopharyngeal swab: local discomfort, vomiting
6. Risks of IV placement: bleeding, infection, thrombosis

Potential risks of genetic testing

Samples obtained for future research may include a search for genetic correlates of COVID-19 susceptibility or severity. Specimens will be labeled by study IDs, rather than names. This information will not be released to participants and will not become part of their medical records. Risks related to discrimination or other problems are deemed highly unlikely.

Alternatives

The alternative to participation in this study is continued standard-of-care clinical management.

Safety monitoring

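### The definition of Completed lets a patient discharged before Day 14 leave the study without a Day 28 status, against the Day 28 assessment planned for everyone

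*Combined protocol and SAP*

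**What the plan says.** - Definitions, item V: "Subjects are considered completed when they are followed through to day 28, if they die before day 28, or are discharged prior to day 14". Any one of the three routes suffices.
- Definitions, item I: "Enrolled: From time consented to participate until designated as a screen failure or have either been discontinued from the study or completed it". Completion therefore ends enrolment.
- Synopsis, Study Design: "The following will be assessed in all subjects", followed by "Safety and efficacy: Day 0 (baseline) to Day 28".
- Design Overview: the primary endpoint is the Day 28 category, and each participant is rated daily on the scale during follow-up.
- Study Procedures: "Day 28 ± 3 1. Vital signs 2. COVID-19 symptom screen (fevers, cough, shortness of breath) 3. Assessment of clinical status". The visit list has no exemption for discharged patients.
- Primary Endpoint: the first two categories are "1. Not hospitalized with resumption of normal activities 2. Not hospitalized, but unable to resume normal activities".
- Secondary Objectives: "To compare in-hospital and 28-day mortality between recipients of the anti-SARS-CoV-2 plasma and control plasma". The secondary analysis section adds: "With a sample size of 220, assuming 20% mortality up to day 28, we expect a total of 43 events".
- Safety monitoring, item 2: vital signs and symptom screens stop at discharge if that comes before Day 28. The Day 28 visit lists both.
- Missing data and non-compliance: little missing data is expected, missingness is compared between arms, and imputation is used in sensitivity analyses. No rule assigns a Day 28 category to a discharged patient.

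**The concern.** The third route to completion has work to do only for a living patient who was not followed to Day 28. A patient discharged early and then followed already meets the first route, and a death meets the second. Read literally, a patient discharged on Day 5 is finished on Day 5, while one discharged on Day 15 must be followed to Day 28. The documents do not explain the difference.

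The Day 28 score cannot be read off the discharge. Categories 1 and 2 differ only in whether normal activities have resumed. A discharged patient may also be back in hospital (3–6) or dead (7) by Day 28. Losing these scores would remove patients chosen for a good early course, and more of them from the active arm if the treatment works. The 28-day mortality comparison and the safety follow-up to Day 28 would have the same gap.

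**Working it through.** **1. The texts side by side.** Take a patient discharged alive on Day 10.

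| Source | Day 28 status required? |
|---|---|
| Definitions, items I and V | No: completed and no longer enrolled on Day 10 |
| Synopsis (all subjects, Day 0 to 28) | Yes |
| Study Procedures, Day 28 ± 3 | Yes |
| Primary endpoint; 28-day mortality | Yes |
| Safety monitoring, item 2 | Vital signs and symptom screen stop on Day 10; scale not mentioned |

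The first row cannot be followed together with the next three.

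**2. The plan's power figure.** From the Primary Analysis section: 146 versus 73 patients, odds ratio 1.7, one-sided 15% level, about 82% power. (The go criterion in the same section uses P < .015; that is a separate matter.) The pooled Day 28 distribution is not given, so I assume 52/10/3/3/2/10/20% for categories 1 to 7.

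Information = n1·n2·N / [3(N+1)²] × (1 − Σp³)

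- 1 − Σp³ = 1 − (0.1406 + 0.0010 + 0.00003 + 0.00003 + 0.00001 + 0.0010 + 0.0080) = 0.849
- Information = 146 × 73 × 219 / (3 × 220²) × 0.849 = 16.08 × 0.849 = 13.65
- Power = Φ(ln 1.7 × √13.65 − 1.036) = Φ(1.961 − 1.036) = Φ(0.924) = 82.2%

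Six other assumed distributions give 77.8% to 85.8%. The stated figure is compatible with its inputs, but cannot be confirmed without the pooled data.

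**3. If early-discharged patients had no Day 28 status and were dropped.** No section plans this, and the early-discharge rate is not in the documents. Simulation: proportional odds, tie-corrected one-sided Mann-Whitney test at 15%, country strata ignored, 20,000 replicates. Early discharge is modelled as the lowest x% of latent severity plus normal noise (SD 0.7, 2 or 4), or as random loss within categories 1–2. Full-data power is 82–83%.

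| Share of 220 lost | Patients | Power | Estimated odds ratio |
|---|---|---|---|
| 5% | 11 | 80–82% | 1.66–1.70 |
| 15% | 33 | 74–80% | 1.59–1.69 |
| 30% | 66 | 63–74% | 1.50–1.67 |
| 45% | 99 | 50–66% | 1.43–1.64 |

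At 30%, missingness is 31–33% in the active arm against 23–27% in control.

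**4. If they were instead carried forward.** At these four loss rates, scoring them all as category 1 costs 0 to 14 points of power, and as category 2 costs 1 to 15 points. The upper end needs about a quarter of early-discharged patients to be readmitted or dead by Day 28 (14% + 10% = 24% in that run). Under three further assumed distributions the largest loss was about 25 points.

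**5. Type I error.** With no treatment effect, and loss driven by severity or random within categories 1–2, rejection stayed at 14–16%. That changes if loss differs by arm for another reason. With identical Day 28 outcomes and loss confined to categories 1–2, as a share of each arm:

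| Loss, active / control | Rejection at nominal 15% |
|---|---|
| 15% / 15% | about 15% |
| 15% / 20% | about 24% |
| 15% / 25% | about 35% |
| 20% / 15% | about 9% |

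**The case against.** The best defence is that Completed is a disposition label. No section says that assessments stop at completion, and no analysis is restricted to completers: efficacy analyses are by intent to treat. The Day 28 endpoint is stated consistently and the visit is scheduled. The power calculation used blinded pooled Day 28 outcomes, so such data were already being collected. The Safety monitoring section names what stops at discharge, and the scale is not on that list.

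Much of this stands. A reader might infer that Day 28 data will be missing; the documents show a contradiction, not a loss. A reader might also infer that early-discharged patients would escape any missing-data or deviation flag. The documents do not support that: an absent score is missing whatever the label, missingness is compared between arms, and monitors check that required data points are recorded.

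The defence does not remove the conflict. Ending enrolment at completion makes the label more than administrative. The existence of pooled Day 28 data does not show that early-discharged patients were contacted or how they were scored. Unspecified imputation is no substitute for a status that one contact could supply.

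**Conclusion.** The definition is wrong as written and conflicts with the primary endpoint it should serve. That conclusion rests on the text alone.

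The size is conditional. If the Day 28 visit is carried out for everyone, the stated power is unaffected. If sites stop at early discharge, the likely result is lost power and an estimate diluted towards no effect: negligible to about 3 points of power at 5% loss, and roughly 10 to 20 points at 30%. These figures depend on assumed discharge rates, distributions and handling.

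It is tempting to conclude either that Type I error is safe or that it is inflated. Neither follows. It holds near 15% when loss depends only on outcome, and can move in either direction when follow-up after discharge differs by arm for other reasons. The Intervention section leaves the clinical study team unblinded, so such a difference is possible; nothing in the documents shows that it occurs.

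**What to change.** 1. In Definitions, item V, delete the limb on discharge before Day 14.
2. Require the seven-category status and vital status at Day 28 ± 3 for every randomised patient who has not withdrawn consent. Obtain them by telephone if the patient has been discharged; if the patient cannot be reached, use record review for vital status and readmission. Records may not separate category 1 from 2, so note the source of each rating.
3. Have the rating made by the blinded outcome assessor already planned, not by the unblinded clinical team.
4. Reconcile Safety monitoring, item 2, with the Day 28 visit, and state that the Day 28 scale assessment does not end at discharge.

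Cost: wording changes in these sections and one contact per early-discharged patient, within a visit already scheduled. At the assumed rates of 5% to 45% that is 11 to 99 contacts. Sample size, treatment and the primary test are unchanged.

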1.1.2. Exclusion Criteria

1. Participation in another clinical trial of anti-viral agent(s)* for COVID-19.
2. Receipt of any anti-viral agent(s)* with possible activity against SARS-CoV-2 <24 hours prior to study drug administration.
3. Mechanically ventilated (including veno-venous (VV)-ECMO) ≥ 5 days.
4. Severe multi-organ failure.
5. History of prior reactions to transfusion blood products meeting definitive case definition criteria, at least severe severity, and probable or definite imputability per National Healthcare Safety Network (NHSN)/Centers for Disease Control and Prevention (CDC) criteria.
6. Known IgA deficiency.
7. Females who are pregnant or breastfeeding.

* Use of Remdesivir as treatment for COVID-19 is permitted.

BACKGROUND AND SCIENTIFIC RATIONALE

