There are currently no proven treatment options for coronavirus disease (COVID-19), which is caused by Severe Acute Respiratory Syndrome Coronavirus 2 (SARS-CoV-2). Human convalescent plasma has been successfully used for treatment of other severe coronavirus infections and thus may provide an option for treatment of COVID-19 and could be rapidly available from people who have recovered from disease and can donate plasma. Passive antibody therapy involves the administration of antibodies against a given infectious agent to a susceptible or ill individual for the purpose of preventing or treating an infectious disease caused by that agent. Experience from prior outbreaks with other coronaviruses, such as SARS-CoV-1, shows that convalescent plasma contains neutralizing antibodies to the relevant virus (Zhang et al., 2005). In the case of SARS-CoV-2, the anticipated mechanism of action by which passive antibody therapy would mediate protection is viral neutralization. However, other mechanisms may be possible, such as antibody dependent cellular cytotoxicity and/or phagocytosis. Convalescent serum was also used in the 2013 African Ebola epidemic. A small 73 non-randomized study in Sierra Leone revealed a significant increase in survival for those 74 treated with convalescent whole blood relative to those who received standard treatment (Sahr et al., 2017). The only antibody type that is currently available for immediate use against SARS-CoV-2 is that found in human convalescent plasma. As more individuals contract COVID-19 and recover, the number of potential donors will continue to increase. When used for therapy, antibody is most effective when administered shortly after the onset of symptoms. The reason for temporal variation in efficacy is not well understood but could reflect that passive antibody works by neutralizing the initial inoculum, which is likely to be much smaller than that of established disease. Another explanation is that antibody works by modifying the inflammatory response, which is also easier during the initial immune response, which may be asymptomatic (Casadevall & Pirofski, 2003). As an example, passive antibody therapy for pneumococcal pneumonia was most effective when administered shortly after the onset of symptoms and there was no benefit if antibody administration was delayed past the third day of disease (Casadevall & Scharff, 1994). For passive antibody therapy to be effective, a sufficient amount of antibody must be administered. When given to a susceptible person, this antibody will circulate in the blood, reach tissues and provide protection against infection. Depending on the antibody amount and composition, the protection conferred by the transferred immunoglobulin can last from weeks to months.

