Exclusion Criteria for Enrollment 1. Participation in another clinical trial of anti-viral agent(s)* for COVID-19 2. Receipt of any anti-viral agent(s)* with possible activity against SARS-CoV-2 < 24 hours prior to plasma infusion. 3. Mechanically ventilated (including VV-ECMO) ≥ 5 days 4. Severe multi-organ failure 5. History of allergic reactions to transfusion blood products per NHSN/CDC criteria 6. Known IgA deficiency 7. Females who are pregnant or breastfeeding. *Use of remdesivir as treatment for COVID-19 is permitted.

Subject Withdrawal

Subjects can terminate study participation and/or withdraw consent at any time without prejudice. II. Randomized subjects who withdraw from the study will not be replaced. III. The investigator may withdraw subjects if they are lost to follow up, non-compliant with study procedures or if the investigator determines that continued participation in the study would be harmful to the subject or the integrity of the study data. IV. Discontinuation of the study: The study sponsor, FDA and IRB all have the right to terminate this study at any time.

Intervention

Subjects will be randomized in a 2:1 ratio, stratified by country, to receive treatment vs. frozen fresh plasma. II. Study drug: The investigational product is anti-SARS-CoV-2 plasma. Patients identified as having recovered from COVID-19 will serve as potential donors. Testing will confirm presence of anti-SARS-CoV-2 antibody prior to donation. Potential donors and samples will be screened for transfusion-transmitted infections (e.g. HIV, HBV, HCV, WNV, HTLV-I/II, T. cruzi, ZIKV) and plasma will be collected using apheresis technology. This is similar to standard blood bank protocols. III. Active arm will receive 1 unit of anti-SARS-CoV-2 plasma. IV. Control arm will receive 1 unit of control plasma. V. The study drug will be in a standard plasma unit bag, with a studyspecific ISBT label and will include the following statement: "Caution: New Drug--Limited by Federal (or United States) law to investigational use." VI. The blood bank will not be blinded to treatment allocation, nor will the clinical study team. VII. The patient and the clinician who will assess the end of treatment outcome will be blinded to treatment allocation.

Randomization

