- Most reactions to plasma are relatively minor and the infusion can generally be continued. Infusion site burning and non-allergic systemic effects can generally be managed with slowing of the infusion. Infusion is generally stopped in cases of itching; participant is treated and then infusion cautiously re-started.
- Severe allergic reactions generally require discontinuation of the infusion. These include:

 - Respiratory compromise: dyspnea, wheezing, stridor, hypoxemia A decrease in systolic blood pressure to < 90 mmHg or $>30\%$ decrease from baseline or a diastolic drop of $>30\%$ from baseline.
 - Tachycardia with an increase in resting heart rate to > 130 bpm; or bradycardia.

Concomitant medications will be documented on the CRF:

- Prescription medications
- Over the counter medications
- Herbal treatments/nutritional supplements
- Blood products

Prohibited Medications:

Any approved or investigational drug* with established or potential activity against SARS-CoV-2 given within 24 hours of plasma infusion. *Concurrent use of Remdesivir as treatment for COVID-19 during the course of the study is permitted.

STATISTICAL CONSIDERATIONS AND DATA MANAGEMENT

Design Overview

This randomized blinded phase 2 trial will assess the efficacy and safety of anti-SARS-CoV-2 plasma among adults with severe COVID-19. Eligible participants will be randomized in a 2:1 ratio to receive anti-SARS-CoV-2 plasma or fresh frozen plasma without known anti-SARS-CoV-2 antibodies. We plan to enroll up to 220 participants (US and Brazil). Each participant will be evaluated at baseline and daily during the follow-up period using a seven-category severity scale: 1. Not hospitalized with resumption of normal activities, 2. Not hospitalized, but unable to resume normal activities, 3. Hospitalized, not requiring supplemental oxygen, 4. Hospitalized, requiring supplemental oxygen, 5. Hospitalized, requiring high-flow oxygen therapy or noninvasive mechanical ventilation, 6. Hospitalized, requiring extracorporeal membrane oxygenation (ECMO), invasive mechanical ventilation, or both, and 7. Death.

According to the inclusion/exclusion criteria, all enrolled participants will have a score ranging 3–6 on this scale at baseline. The primary study endpoint is defined as the Day 28 outcome on the scale.

Safety will also be evaluated daily. Secondary endpoints include:

- SARS-CoV-2 PCR positivity from nasopharyngeal swab, collected on baseline (Day 0), Days 7, and 14.

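### The 24-hour look-back leaves patients who received off-trial convalescent plasma or other anti-SARS-CoV-2 antibody earlier than that eligible, which can dilute the Day 28 contrast

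*Combined protocol and SAP*

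**What the plan says.** The protocol lists its exclusions twice: in section 1.1.2 of the synopsis, and under Exclusion Criteria for Enrollment in the Investigational Plan. In each list, two items concern earlier anti-SARS-CoV-2 treatment.

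- Item 1: "Participation in another clinical trial of anti-viral agent(s)* for COVID-19". This reaches treatment given inside another trial only.
- Item 2 in the synopsis: "Receipt of any anti-viral agent(s)* with possible activity against SARS-CoV-2 <24 hours prior to study drug administration". The Investigational Plan has the same rule with slightly different wording: "Receipt of any anti-viral agent(s)* with possible activity against SARS-CoV-2 < 24 hours prior to plasma infusion".

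Both items carry an exemption, worded in the Investigational Plan as "Use of remdesivir as treatment for COVID-19 is permitted".

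Prohibited Medications repeats the window: "Any approved or investigational drug* with established or potential activity against SARS-CoV-2 given within 24 hours of plasma infusion".

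The one criterion that touches earlier transfusion is item 5, worded in the Investigational Plan as "History of allergic reactions to transfusion blood products per NHSN/CDC criteria". It excludes earlier reactions, not earlier receipt.

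The term for antiviral agents is not defined. Potential benefits of treatment, under Risks and Benefits, does use that word for the study plasma: "The potential benefits of antiviral treatment with anti-SARS CoV-2 plasma in patients with severe COVID-19 is unknown".

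On persistence, Background and Scientific Rationale says that, depending on the amount and composition of antibody, "the protection conferred by the transferred immunoglobulin can last from weeks to months".

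**The concern.** The trial asks whether plasma with anti-SARS-CoV-2 antibody does better than plasma without it. The control product is protected accordingly: Control arm plasma restricts it to collections from before the end of 2019. Nothing gives the patient's own recent treatment the same protection. A control patient who had convalescent plasma two days earlier may carry the test treatment, and an active patient in the same position receives a second unit.

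There is time for this to happen. The qualifying PCR may be up to 14 days old at randomization, patients ventilated for less than 5 days may enter, and infusion may follow randomization by up to 48 hours. Randomization is stratified by country only, the screening and baseline lists contain no antibody test, and no analysis by earlier antibody receipt is planned.

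At stake is the size of the Day 28 effect, and with it the chance of a false no-go. The safety comparison is also blurred: for these patients it becomes two units of convalescent plasma against one, in a trial that names antibody-dependent enhancement as a concern.

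**Working it through.** **1. Is such a patient eligible?** Take a patient given convalescent plasma outside a trial 48 hours before study infusion, without a transfusion reaction.

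- Item 1 does not apply, because there was no other trial.
- Item 2, if plasma counts as an antiviral agent: 48 hours is outside the 24-hour window, so it does not apply.
- Item 2, if plasma does not count: it does not apply at any interval.
- Item 5 does not apply, because there was no reaction.
- Prohibited Medications: 48 hours is outside its window.

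The patient is eligible on either reading. The undefined term matters only for receipt inside 24 hours.

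**2. The plan's own power figure.** Primary Analysis states about 82% power for N = 219 (146 vs 73), odds ratio 1.7, one-sided 15% level. The pooled Day 28 distribution behind it is not given. Whitehead's proportional-odds formula is

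power = Φ( √[N·A·θ²·(1 − Σp³) / (3(A+1)²)] − z ), with A = 2, θ = ln 1.7 = 0.5306, z = 1.036.

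For an assumed distribution over categories 1–7 of 50/10/5/5/2/8/20%, 1 − Σp³ = 0.865. The root is √(219 × 2 × 0.2816 × 0.865 / 27) = 1.988, and Φ(1.988 − 1.036) = 82.9%. Four assumed distributions, with 1 − Σp³ from 0.78 to 0.98, give 80% to 86%, so the stated figure is reachable.

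**3. Dilution by simulation.** Assumed control distribution: 30/20/5/8/5/12/20%. The active arm follows by odds ratio 1.7, with a tie-corrected Mann-Whitney test, 146 vs 73, one-sided 15%. A share f of both arms has had antibody before. Two assumptions are compared:

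- No contrast: prior recipients have the treated distribution in either arm.
- Half effect: in prior recipients the study unit adds half of ln 1.7, that is 0.265, or an odds ratio of about 1.30.

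| f | no contrast | half effect |
|---|---|---|
| 0 | 85% | 85% |
| 5% | 82% | 84% |
| 10% | 80% | 82% |
| 20% | 73% | 79% |

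At f = 1–2% the loss is about one point at most, even with no contrast.

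**4. Cross-check in closed form.** With no contrast, θ is multiplied by (1 − f). From the 82.9% in step 2:

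- f = 5%: Φ(1.889 − 1.036) = 80.3%
- f = 10%: Φ(1.789 − 1.036) = 77.4%
- f = 20%: Φ(1.590 − 1.036) = 71.0%

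The starting point is lower but the losses are similar.

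**5. Calibration.** In step 3 the active-arm odds of death are 0.25 / 1.7 = 0.147, a risk of 12.8%. Pooled mortality is (146 × 0.128 + 73 × 0.20) / 219 = 15.2%, below the 20% assumed under Secondary and Ancillary Analyses. The table therefore shows the order of the loss; it is not a recalculation of the plan's power.

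**The case against.** The strongest reply is that the consequence is speculative and small, and much of that stands.

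- **Frequency.** The documents give no rate of off-trial antibody use at the sites. The 20% row has no support in them, and if use is rare the loss is negligible.
- **Persistence.** A reader might infer that the protocol says antibody from one unit lasts weeks to months in these patients, so that its sections contradict each other. It does not say so. The sentence is general background: it says that protection can last that long, in a susceptible person and depending on amount and composition. It gives reason to doubt a 24-hour look-back for antibody products; it does not prove that any given patient is still protected.
- **Contrast.** A reader might infer that prior recipients have no contrast at all. That is the worst case. Rationale for dosing takes antibody delivered as proportional to dose, under which two units against one is still a contrast. Hence the second column of the table.
- **Direction.** A reader might infer bias in favour of an arm. Receipt before randomization is balanced in expectation, so it dilutes only.
- **Design choice.** Broad eligibility is defensible in phase 2.

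What does not stand is the suggestion that existing text closes the gap. Listing blood products among concomitant medications records exposure but does not exclude it. Nor does the protocol give an investigator a ground for refusing such a patient.

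**Conclusion.** The concern holds as an eligibility gap. On either reading of the undefined term, off-trial convalescent plasma or another anti-SARS-CoV-2 antibody product given more than 24 hours before study infusion does not exclude a patient.

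The effect is attenuation towards no difference. With the assumed distribution and baseline power of 85%, the loss at 5–20% prior recipients is about 3 to 12 points if they have no contrast, and about 1 to 6 points if the second unit adds half the effect. These sizes rest on an assumed distribution, an unknown frequency and the 15% level. Primary Analysis separately sets the go decision at one-sided P < .015, where the step 2 inputs give only about 39% to 48% power before any dilution. That conflict is a different matter, but the probability of a false no-go cannot be fixed until it is settled.

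This is a cheap improvement worth making. It does not invalidate the design.

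**What to change.** 1. Add to both exclusion lists: prior receipt, for this illness, of SARS-CoV-2 convalescent plasma, hyperimmune globulin or anti-SARS-CoV-2 monoclonal antibody, checked at eligibility.
2. An exclusion checked at eligibility cannot cover the interval of up to 48 hours before infusion. Record any antibody receipt in that interval from the concomitant-medication entries already scheduled at Baseline and Day 0, and keep those patients in the intent-to-treat analysis.
3. Add a sensitivity analysis that omits, in both arms, patients who received antibody before study infusion. Treat it as supportive: receipt after randomization is not protected by randomization, and Intervention states that the clinical study team is not blinded. Recoding controls as treated in the as-treated analysis would be more open to confounding and is not recommended.
4. The sponsor should reconcile the 24-hour window with the Background statement for antibody products. No clinical rule for the period after infusion is proposed here. The Day 1 to Day 28 visit lists include no concomitant-medication item, so tracking later non-study antibody may need new data collection.

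The cost is one line in each list, one derived flag and one sensitivity analysis. The downside is that a few patients become ineligible.
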